## **18. DATA ANALYSIS PLAN – To be performed at UVA**

### Data harmonization, management and analysis

1. Develop data management and statistical analysis plan.
2. Work with the team and CTSI at URMU closely to design a unified management system for data collection, transfer between the study site and management.
3. Data oversight and monitoring during data collection and integration.
4. Harmonize the study data elements and variables from clinical and laboratory and biochemical data
5. Validate data quality and perform cleaning process.
6. Work closely with the PI and clinical investigators to determine appropriate statistical methods and machine learning algorithms for the clinical hypotheses. Cutting-edge statistical methods and innovative data science tools will be considered or adopted.
7. Prepare the analytical datasets and perform pre-stated statistical analyses.
8. Prepare the final results for manuscript writing and submission, conference presentations and publications.

**Power calculation:** The primary outcome of interest in this study is plasma 8-isoprostane, one of the markers of oxidative stress. Based on: 1) the inverse correlation between 8-isoprostane and eGFR (Figure 1 of Cottone *et al.*), 2) the average 8-isoprostane for hypertensive patients of  $262 \pm 137$  pg/ml, 3) a range from 350 to 550 pg/ml for CKD Stages 3-4 patients, and 4) therefore the assumption that the average 8-isoprostane would be  $400 \pm 150$  pg/ml in placebo group, we hypothesize that Avmacol ES would reduce by 25%, approximately at 300 pg/mL.

According to power calculations, the minimum number of participants that need to be recruited is 88. To address the challenges of recruiting patients with stage 4 CKD, there will not be a fixed proportion of patients with CKD stage 3 and 4 that will make up the final 88. However, an equal number of subjects

regardless of CKD stage (44 each) will be assigned by the IDS to the Avmacol ES and placebo arm of the study. **The final 88 will include the ones already enrolled.**

If study participants drop out, additional patients with CKD stage 3 or 4 will be recruited to reach this number. For example, if 8 out of 88 participants drop out, 8 more would be enrolled so the final number of enrollments would be 96.

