If a CKD stage 4 patient drops out, a CKD stage 3 patient may be enrolled to make up for the drop-out to reach the total of 88 study participants. Treatment assignments will be performed by the IDS, and the study team will remain blinded.

With 44 patients in Avmacol ES group and 44 in placebo group who would complete the study, we expect to have power to detect the difference in 8-isoprostane between the two groups. The power analysis was performed using two-sample *t*-test with 5% type I error. The effect size is considered close to medium effect, which is appropriate for this pilot study as we intend to establish preliminary evidence of treatment effect of Avmacol ES. As mentioned above, *the Kidney Clinic in AC3 sees ~ 800-900 patients with CKD a month and ~ 60% of patients are in the CKD Stages 3-4 stages. Thus, in addition to Highland Hospital, we should be able to easily achieve our recruitment target.*

In the event that patients drop out the study due to relocation or loss to follow up, we will recruit additional patients. Based on the number of dropouts at 12 months into the study, we will recruit an extra number of patients commensurate with the dropout rate such that we will have the anticipated number of patients (44 in each group) who will complete the study in 24 months.

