**Statistical Analysis:** The data for safety and feasibility assessment will be summarized descriptively with respect to adverse events and compliance with Avmacol ES intake. The difference between the two treatment groups will be evaluated with Chi-square test, and logistic regression if necessary. Distributions of outcome variables will be examined graphically for asymmetry and for outliers. If a lack of symmetry is noted, the variable will be transformed before analysis. The group-specific data will be summarized and reported as mean  $\pm$  SD or median (interquartile range) for continuous measures and as frequency and percentage for categorical measures and their differences will be compared using two-sample *t*-tests or Chi-square test. Those baseline characteristics that are significantly different between the 2 groups will be adjusted in the subsequent analyses. Since plasma 8-isoprostane will be measured at baseline, 1, 3, and 6 months, the effect of Avmacol will be explored at each time point with *t*-test or linear regression to detect an early effect of Avmacol at 1 or 3 months and to determine if such effect will be sustained at 6 months while the patients remain on Avmacol. The effect of Avmacol on longitudinal plasma 8-isoprostane measures will be analyzed with linear mixed effects model, adjusting for potential confounding factors such as age, initial BMI, and baseline characteristics identified in the preliminary analysis. Other factors that might affect the results (such as physical activity and dietary intake) will also be examined. Similar analyses will be performed for the secondary outcomes, including plasma IL-6, urine 8-isoprostane, and urine nephrin. We will also explore the effect of Avmacol on eGFR with linear mixed effects modeling by comparing the slope of eGFR decline between groups, and to the previous 6 months within group, and the effect of *GSTM1* genotype on the response to Avmacol. Additionally, penalized regression and machine learning methods such as random forests algorithm will be considered and applied to fully evaluate the treatment effect and predictability of Avmacol and other important predictors on the outcomes.

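### Whether an early effect on plasma 8-isoprostane lasts to month 6 is assigned to separate visit-by-visit tests, none of which examines whether the effect changed

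*Combined protocol and SAP*

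**What the plan says.** Section 18 names the outcome: "The primary outcome of interest in this study is plasma 8-isoprostane, one of the markers of oxidative stress". It is measured at baseline and at months 1, 3 and 6. The Statistical Analysis paragraph says that "the effect of Avmacol will be explored at each time point with" a t-test or linear regression, and the same sentence gives the purpose: "to detect an early effect of Avmacol at 1 or 3 months and to determine if such effect will be sustained at 6 months", with patients still taking the supplement.

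The next sentence plans a linear mixed effects model for the repeated 8-isoprostane values. It lists covariates (age, initial BMI, baseline characteristics found to differ). It does not say how visit enters the model, names no treatment-by-visit term and no contrast between visits, and does not link the model to the durability question. A comparison of slopes between arms is named only for eGFR. The section does not define what counts as sustained. Similar analyses are planned for plasma IL-6, urine 8-isoprostane and urine nephrin.

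**The concern.** The visit-wise tests do not match the question. A test at month 6 has the null hypothesis of no difference between arms at month 6. A statement about whether an early effect was kept concerns the difference between two treatment effects, one early and one at month 6. Significance at month 3 without significance at month 6 is not evidence that the effect faded, because the two estimates may be almost equal. Significance at both visits is not evidence that the size of the effect held.

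The issue does not depend on which visit is primary or on multiplicity: it would remain if month 6 alone were primary. It matters because this is the primary outcome, and Section 10 says that positive results would support a larger and longer study. Whether the effect lasts during continued intake is part of that argument.

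**Working it through.** **Inputs from Section 18.** Placebo mean 400 and SD 150 pg/mL; "we hypothesize that Avmacol ES would reduce by 25%, approximately at 300 pg/mL"; 44 completers per arm; "The power analysis was performed using two-sample *t*-test with 5% type I error"; "The effect size is considered close to medium effect".

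**Assumptions, because the plan is silent.** Two-sided test; SD 150 in both arms and at every visit; equal correlation *r* between visits of 0.3, 0.5 or 0.7; normal data; nothing missing; no baseline adjustment.

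**Step 1, the plan's own figure.** The difference is 400 − 300 = 100 pg/mL, so d = 100/150 = 0.667. With 44 per arm the two-sample t-test has power of about 87%. The plan states no target power, so its total of 88 can be neither confirmed nor called wrong. A conventional medium effect, d = 0.5, is 75 pg/mL and has power of about 64%.

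**Step 2, reading durability from visit-wise significance.** Simulation of 40,000 trials per scenario. Early effect: significant benefit at month 1 or month 3. Called sustained: also significant at month 6. Called lost: not significant at month 6.

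| True effect at months 1, 3, 6 (pg/mL) | Result | r = 0.3 | r = 0.5 | r = 0.7 |
|---|---|---|---|---|
| 100, 100, 100 | early effect, then called lost (all trials) | 11.7% | 10.6% | 8.6% |
| 75, 75, 75 | early effect, then called lost (all trials) | 26.5% | 22.3% | 17.3% |
| 75, 75, 75 | called lost, among trials with an early effect | 31.9% | 28.2% | 22.8% |
| 100, 100, 50 | called sustained, among trials with an early effect | 34.3% | 35.3% | 36.3% |

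Repeated runs of the last row agree within about one percentage point; the range is reported as about 35-37%.

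**Step 3, the contrast that addresses change.** Take month 6 minus the mean of months 1 and 3.

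- SD per patient = 150 × √(1.5 × (1 − r)) = 153.7, 129.9 and 100.6 pg/mL.
- SE of the between-arm difference = SD × √(2/44) = 32.8, 27.7 and 21.5 pg/mL.
- 95% CI half-width = 1.988 × SE = 65, 55 and 43 pg/mL.
- Under a constant effect, a 5% test of this contrast rejects in 5% of simulated trials.
- For a fall from 100 to 50 pg/mL, its power is about 33%, 43% and 63%.

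The contrast estimates the right quantity, but 88 patients estimate it imprecisely. The half-width is similar in size to the 50 pg/mL loss it would need to show.

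**The case against.** The strongest reply is that the plan contains no decision rule of this kind. It calls the visit-wise analyses exploratory, does not say that sustained means p < 0.05 at month 6, and allows regressions whose estimates could be compared by eye. This stands. The error rates in the working describe one likely way of using the tests, not a rule that the sponsor wrote.

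A second reply is that sustained may simply mean still present at month 6. A month 6 comparison between arms answers that question, and calling a halved effect sustained is then correct. This also stands, and it is a reason to define the word.

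Third, a reader might infer that constant effects would often be declared lost. At the plan's own effect the rate is about one trial in ten. It approaches one in four only near 0.5 SD, whose support in the plan is the phrase about a medium effect. Adjusting for baseline 8-isoprostane, which the plan does not name as a covariate, would lower the rate further: to roughly 9%, 5% and 1% at the planned effect if the baseline correlation is 0.3, 0.5 and 0.7.

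Fourth, as a test the contrast is no better at flagging a real halving. It does so in about 32-64% of trials, while the visit-wise reading labels the same halving lost in about 63-65% of trials with an early effect. This rules out replacing one significance test with another. It does not rescue the visit-wise tests, which give no estimate of change with its uncertainty.

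Finally, the mixed model could carry the contrast, and Section 18 lists the development of an analysis plan as a task. But the text as it stands assigns the durability question to the visit-wise tests and gives the model no term that could answer it.

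**Conclusion.** The concern holds in a limited form. The plan links the durability question to visit-wise tests of zero effect, and no listed analysis of 8-isoprostane estimates whether the treatment effect changed between visits. If durability is read from significance at each visit, a constant effect is called lost in about 9-12% of trials at 0.667 SD and 17-27% at 0.5 SD. A halving from 0.667 to 0.333 SD is called sustained in about 35-37% of trials with an early effect, which is wrong only if sustained means undiminished. These figures rest on the assumed correlations, equal SDs, complete data and no baseline adjustment.

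The documents do not support the stronger reading that a written rule produces wrong durability conclusions in both directions. The primary outcome, the sample size and the data collected are unaffected. The change is still worth making, because it answers a question that the plan itself asks and costs almost nothing.

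**What to change.** In Section 18, make three changes.

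1. In the planned mixed model for 8-isoprostane, enter visit as a categorical factor with treatment-by-visit terms. Report the treatment effect at months 1, 3 and 6, and the contrast of month 6 minus the mean of months 1 and 3, each with a 95% confidence interval.
2. State before unblinding whether sustained means still present at month 6 or not materially smaller than the early effect. If the second, state how much loss would count as material.
3. Describe durability from the estimates and intervals. Do not base it on which visits reach p < 0.05, and do not treat a non-significant contrast as proof that the effect was kept.

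Apply the same wording to the secondary biomarkers that are to be analysed similarly.

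The cost is a few sentences and one contrast from a model already planned, with no new visits or samples. The drawback is a more cautious durability statement: an interval of about ±43 to ±65 pg/mL will often be compatible both with no change and with loss of half the planned effect.

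### The mixed model for plasma 8-isoprostane does not say how month 0 is handled, how visit is coded or which contrast is the effect of Avmacol, and so permits diluted or inefficient estimates

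*Combined protocol and SAP*

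**What the plan says.** Section 18 (Power calculation) names the primary outcome: "The primary outcome of interest in this study is plasma 8-isoprostane, one of the markers of oxidative stress". It assumes a placebo mean of 400 pg/mL with SD 150, and "we hypothesize that Avmacol ES would reduce by 25%, approximately at 300 pg/mL". The sizing method is a two-sample t-test at 5% type I error with 44 completers per arm. No power figure is given.

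Section 18 (Statistical Analysis) gives the visits: "Since plasma 8-isoprostane will be measured at baseline, 1, 3, and 6 months". A first set of comparisons is planned visit by visit: "the effect of Avmacol will be explored at each time point with" either a t-test or a linear regression. The longitudinal analysis comes next: "The effect of Avmacol on longitudinal plasma 8-isoprostane measures will be analyzed with linear mixed effects model". The covariates of that model are described in these terms: "adjusting for potential confounding factors such as age, initial BMI, and baseline characteristics identified in the preliminary analysis". The rule for choosing baseline covariates is: "Those baseline characteristics that are significantly different between the 2 groups will be adjusted in the subsequent analyses". Similar analyses are planned for plasma IL-6, urine 8-isoprostane and urine nephrin. For eGFR alone the contrast is named: the mixed model is used "by comparing the slope of eGFR decline between groups".

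For 8-isoprostane the plan does not state which visits form the outcome, whether time is linear or categorical, whether there is a treatment-by-visit term, the covariance structure, or the contrast to be reported.

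**The concern.** The only set of 8-isoprostane measures that the plan describes includes month 0, when no treatment effect is possible. Baseline 8-isoprostane is not named as a covariate. Under the imbalance rule it is sure to enter only if the arms happen to differ significantly on it, although its value as a covariate comes from its correlation with later values and not from imbalance.

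Several models fit the wording, and they estimate different quantities. A single treatment term over all four visits averages in a visit with zero effect. A straight line from month 0 does not fit an early, sustained fall, which is one of the patterns that Section 18 sets out to detect. A plain change-from-baseline contrast estimates the right quantity but uses the baseline value inefficiently.

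The choice matters because Section 10 presents the trial as a possible rationale for a larger and longer study, so the size of the effect is a main product. Section 18 leaves the choice of methods to discussion with the investigators, and Section 14 allows unblinding before analysis. If the contrast is not fixed beforehand, it could be chosen with assignments known.

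**Working it through.** **Inputs from the documents (Section 18).** Difference 400 − 300 = 100 pg/mL; SD 150; 44 per arm; visits at months 0, 1, 3 and 6; 5% type I error.

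**Assumptions not in the documents.** Two-sided test; complete data; equal SD at all visits; compound symmetry with within-patient correlation ρ = 0.3, 0.5 or 0.7; for the main example, an effect of 0, 100, 100, 100 pg/mL at the four visits. Power is by noncentral t (86 df, or 85 where baseline is used), with the covariance treated as known.

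**The plan's own figure.** For a t-test at one visit, SE = √(2 × 22,500 / 44) = 31.98, noncentrality 100 / 31.98 = 3.127, power 87.1%. By the normal formula 80% power needs 36 per arm, 85% needs 41 and 90% needs 48. Since no power is stated, 88 can be neither confirmed nor refuted.

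**Estimates and variances.** In each case SE = √(2 × V / 44), with V the per-patient variance.

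1. *Treatment term pooled over four visits.* Estimate (0 + 100 + 100 + 100) / 4 = 75. V = 22,500 × (1 + 3ρ) / 4. At ρ = 0.5, V = 14,062.5, SE = 25.28, noncentrality 2.966.
2. *Straight-line group-by-month contrast, free intercepts.* Mean time is 2.5, deviations are −2.5, −1.5, 0.5 and 3.5, and their sum of squares is 21. Slope = 100 × (−1.5 + 0.5 + 3.5) / 21 = 11.90 per month, or 71.4 at month 6. V = 36 × 22,500 × (1 − ρ) / 21. At ρ = 0.5, SE = 29.61, noncentrality 2.412.
3. *Treatment by categorical visit, unconstrained, change to month 6.* Estimate 100. V = 2 × 22,500 × (1 − ρ).
4. *Treatment by categorical visit, baseline means constrained equal (or baseline as covariate), month 6.* Estimate 100. V = 22,500 × (1 − ρ²). At ρ = 0.5, SE = 27.70, noncentrality 3.611.
5. *As 4, averaged over months 1, 3 and 6.* Estimate 100. V = 22,500 × ((1 + 2ρ)/3 − ρ²).

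| Contrast | Estimate (pg/mL) | Power, ρ = 0.3 | 0.5 | 0.7 |
|---|---|---|---|---|
| 1. Pooled term, four visits | 75 | 92.0% | 83.5% | 75.0% |
| 2. Linear slope × 6 | 71.4 | 52.2% | 66.5% | 86.9% |
| 3. Change to month 6, unconstrained | 100 | 74.3% | 87.1% | 97.9% |
| 4. Month 6, baseline constrained | 100 | 90.0% | 94.6% | 99.1% |
| 5. Average of months 1, 3, 6, baseline constrained | 100 | 99.6% | 99.8% | >99.9% |
| Single-visit t-test | 100 | 87.1% | 87.1% | 87.1% |

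**Other time courses.** Percentages are of the month-6 effect.

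| Effect at months 0, 1, 3, 6 | Pooled term | Linear slope × 6 |
|---|---|---|
| 0, 1, 1, 1 | 75% | 71% |
| 0, 0.5, 1, 1 | 62.5% | 93% |
| 0, 1/6, 1/2, 1 (linear growth) | 42% | 100% |

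So, for effects that are constant or build up, the pooled term recovers 42–75% of the month-6 effect and the slope 71–100%. Against the average of months 1, 3 and 6, the pooled term is always 75%, because it divides the same sum by 4 instead of 3. Contrasts 3 and 4 recover 100% of the month-6 effect under any time course.

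**The case against.** A reader might infer that the plan takes month 0 as one of four outcomes, and so will understate the fall by about a quarter and lose power. The documents do not support that.

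- The list of visits introduces the per-visit tests. The mixed-model sentence does not define its outcome visits, and no pooled treatment term is stated. Section 4 (Aim 2) speaks of comparing biomarkers between groups and with baseline within groups, which treats baseline as a reference.
- Month 0 among the outcomes does not by itself dilute anything. Contrasts 3 and 4 can both keep it there and recover the full effect.
- The slope contrast is named only for eGFR. The statement about similar analyses carries the 8-isoprostane methods forward to other biomarkers; it does not carry the eGFR slope back.
- The 71% and 75% figures, taken against the month-6 effect, need an immediate and constant effect. The plan treats early onset and persistence as questions to explore.
- Loss of power against the t-test depends on a correlation that the documents do not give. The pooled term beats the t-test at ρ = 0.3, and the slope about equals it at 0.7.
- The per-visit tests estimate the 400 v 300 difference undiluted, so a later trial would not have only a diluted figure.

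All of this stands against a claim of demonstrated bias. It does not supply the missing specification. Section 18 lists developing an analysis plan as a task, but that entry settles none of the open choices.

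**Conclusion.** The concern holds as under-specification of the longitudinal analysis of the primary outcome, with a better method available from data already collected. The wording is compatible with contrasts that recover anywhere from 42% to 100% of the month-6 effect over the constant or increasing time courses tried. It is also compatible with an unbiased change contrast that, at an assumed ρ of 0.3, has 74.3% power against 87.1% for the single-visit t-test. The constrained-baseline or baseline-adjusted model recovers the full month-6 effect and has more power than the t-test at each correlation examined (90.0/94.6/99.1% at ρ = 0.3/0.5/0.7).

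The power figures rest on SD 150, a 100 pg/mL difference, complete data on 44 per arm, compound symmetry and the assumed correlations. The 75 and 71 pg/mL figures also need an effect that is constant from month 1, and are examples only. That the recommended contrast is undiluted does not depend on the time course.

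**What to change.** In Section 18 (Statistical Analysis), state the following for plasma 8-isoprostane:

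- The mixed model has visit as a category and treatment by visit. Month 0 stays in the outcome vector with the two arms' baseline means constrained equal. Alternatively, months 1, 3 and 6 are the outcomes and baseline 8-isoprostane is a covariate whether or not the arms differ at baseline.
- The effect of Avmacol is the Avmacol-minus-placebo difference at month 6, or averaged over months 1, 3 and 6. Choose one before unblinding and name it as the reported contrast.

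Use the same form for plasma IL-6, urine 8-isoprostane and urine nephrin. Leave the eGFR slope analysis as it is.

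The cost is a few sentences of wording. Data, visits, assays and software are unchanged, and there is no material downside.

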### 4. STUDY DESIGN

#### **Aim 1. To test whether Avmacol ES will be safe and well tolerated in CKD patients.**

In the PK phase (IRB protocol study 6759), we established that 4 tablets of Avmacol ES is an appropriate and tolerable dose for CKD Stages 3-4 patients. We will enroll 88 patients from the Kidney Clinic in AC3, Highland Hospital, Brockport, St. James, and FF Thompson who have CKD stages 3-4 and a steady decline in estimated glomerular filtration rate (eGFR)  $\geq 3$  mL/min/m^2/year in the previous 12 months despite receiving standard of care. Patients will be randomized in a 1:1 Avmacol ES:placebo ratio. They will be given oral Avmacol or placebo for 6 months. Any side effects or adverse effects will be documented, and compliance to the study treatment will be monitored by tablet count at study visits. A comprehensive metabolic panel will be obtained as part of standard of care at each visit to monitor for any potential metabolic, renal or liver toxicity. The effect of *GSTM1* genotype on tolerability of Avmacol ES will be determined.

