#### **Aim 2. To test whether Avmacol ES will improve clinical and biochemical parameters.**

At the baseline visit (month 0) and each subsequent clinic visits (typically 3 - 4 month intervals, blood pressure will be recorded, and a comprehensive metabolic profile, and urinary albumin and protein/creatinine ratio will be obtained as standard of care for patients with CKD Stages 3-4. In addition, at the baseline visit, the 1st month visit, and the two subsequent visits (3-4 months intervals), research lab work including markers of oxidative stress and inflammation, and podocyte damage (plasma and urine 8-isoprostane and plasma interleukin-6, and urine nephrin respectively), will also be assessed and compared between groups and to baseline within groups. Peripheral blood mononuclear cells (PBMCs) will also be obtained for analysis of mRNA levels of cytoprotective enzymes. This pilot study will allow us to begin to explore the effect of Avmacol ES on biomarkers of oxidative stress and inflammation. We will also explore the effect of Avmacol on the rate of decline of eGFR and compare between groups, and to the previous 6 months within group. The effect of *GSTM1* genotype on clinical and biochemical response will also be

assessed.

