### 5. INCLUSION AND EXCLUSION CRITERIA

#### **Inclusion Criteria:**

- Age  $\geq 18$  years and  $\leq 80$  years
- Estimated glomerular filtration rate (eGFR)  $\geq 20$  and  $< 60$  mL/min/1.73m^2 and a decline in eGFR of  $\geq 3$  mL/min/1.73m^2/year in the previous 12  $\pm$  2 months
- Able to provide consent
- Able to swallow Avmacol ES or placebo tablets

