## **8. STUDY PROCEDURES**

A total of 4 in-person visits and 3 phone call visits will occur for the Phase II study. The baseline (month 0), first-, third-, and sixth-month visits are expected to last about 1 hour and will occur at the labs at SMH, and AC3 clinic in SMH, or Kidney clinic in Highland Hospital. The second-, fourth-, and fifth-month visits are anticipated to last about 30 minutes on the phone.

A 6-month **randomized, double-blind, placebo-controlled study** with Avmacol ES will be conducted. The study will include:

1. Pre-screening
2. Informed consent and buccal swab to determine GSTM1 genotype
3. Randomization: Patients will take the medication or placebo for 6 months, and continue to receive standard of care for CKD
4. Clinic visits for blood pressure (BP) check, labs (urine, blood) at baseline (month 0), months 1, 3, and 6. Kansas City Cardiomyopathy and NIH PROMIS questionnaires administered in-person via paper or REDCap. Side effects and adverse events (AEs) assessment; gastrointestinal (GI), heart failure symptoms
5. Phone call visits and paper/REDCap questionnaires at months 2, 4, 5: Kansas City Cardiomyopathy and NIH PROMIS questionnaires will be offered via REDCap surveys or paper copies depending on participant preference. Side effects and adverse events (AEs) assessment; gastrointestinal (GI), heart failure symptoms will be monitored

Subjects will be provided a yearly calendar to mark the days they consume the tablets and will be asked to have it available with them at each visit to monitor tablet compliance. They will also be provided a reusable medication tracker called Take-n-slide. This product is provided free of cost by the company in exchange for a simple, 5-question survey from the study subjects. The survey will be conducted approx. 1 month after the study subjects start taking the tablets, and they can keep the tracker afterwards for their use.

**1. Pre-Screening:** Demographics and medical history will be obtained using eRecord EMR. Each week, using the inclusion and exclusion criteria, the research coordinator will screen for patients who have a scheduled appointment in our Kidney Clinic within the next 4 weeks.

- The eGFR result should be within a 60-day window at the time of screening. If eGFR testing was performed longer than 60 days, the research coordinator will reach out to the patient's provider to ask when another eGFR will be obtained as part of the patient's standard of care and will follow

up.

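### Comparing on-study eGFR slope with the previous 6 months within each group is biased toward apparent slowing in both arms, because patients are selected on an observed eGFR fall over an overlapping period

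*Combined protocol and SAP*

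**What the plan says.** Section 5 (Inclusion Criteria) admits patients whose eGFR is at least 20 and below 60 mL/min/1.73m² and has fallen by at least 3 mL/min/1.73m² per year over the previous 12 ± 2 months. Section 4, Aim 1, describes the same requirement as "a steady decline in estimated glomerular filtration rate (eGFR") of at least 3 per year "in the previous 12 months despite receiving standard of care". Neither place says how the decline is calculated or how many values it needs.

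Section 8 (Pre-Screening) sets the age of the latest value: "The eGFR result should be within a 60-day window at the time of screening". No confirmatory value and no run-in is required.

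On-study samples are "labs (urine, blood) at baseline (month 0), months 1, 3, and 6". Section 4, Aim 2, plans to explore the eGFR decline rate and "compare between groups, and to the previous 6 months within group". Section 18 (Statistical Analysis) repeats this with a linear mixed effects model, "by comparing the slope of eGFR decline between groups, and to the previous 6 months within group".

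The primary outcome is plasma 8-isoprostane (Section 18, Power calculation). The named secondary outcomes are plasma IL-6, urine 8-isoprostane and urine nephrin. Slower kidney disease progression is nevertheless the first element of the hypothesis in Section 1.

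**The concern.** A patient can meet the entry criterion because kidney function is truly falling fast, because the first value was high by chance, or because the last value was low by chance. Any group selected this way contains an excess of chance-low last values. The slope over the 6 months ending at that value is therefore steeper than the patients' true slope. Later slopes return to the true value, and the difference looks like slowing.

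Shortening the prior window from 12 to 6 months does not help. The same low value ends both windows, and over 6 months its error is divided by half a year instead of a whole one. If that value also serves as month 0, its error flattens the on-study slope as well.

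The documents nowhere mention regression to the mean, and they do not restrict the within-group comparison to description. With 44 patients per arm followed for 6 months, a favourable change within the Avmacol arm could be read as support for the Section 1 hypothesis, and Section 10 says positive results would justify a larger and longer trial of progression.

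**Working it through.** The plan gives no figure for this comparison to reproduce. Its only sample-size figure (88, or 44 per arm) concerns 8-isoprostane.

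**Inputs from the documents.** Threshold of 3 mL/min/1.73m² per year over 12 months (Sections 4 and 5); prior window of 6 months (Sections 4 and 18); on-study values at months 0, 1, 3 and 6 (Section 8); 44 per arm (Section 18).

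**Assumptions.** True slope *b* is normal with mean μ = -2, -3 or -5 and SD 3. Visit-to-visit SD σ is 1 to 4. There is no treatment effect. Selection uses two points: eGFR(-12) minus eGFR(0) is at least 3. The prior slope runs from month -6 to the qualifying value at time 0.

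**Step 1: error in the qualifying value.** The observed fall has mean -μ and SD V = √(3² + 2σ²). With c = (3 + μ)/V and λ = φ(c)/(1 - Φ(c)), the mean error of the qualifying value among selected patients is -σ²λ/V, and their mean true slope is μ - 9λ/V.

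**Step 2: prior slope.** It equals *b* + 2 × (error at 0 minus error at -6), so its bias is -2σ²λ/V. A further value at month -3 has zero weight in a least-squares slope and changes nothing.

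**Step 3: on-study slope, fresh month 0.** The errors are new, so the slope is unbiased. Spurious slowing = 2σ²λ/V.

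**Step 4: on-study slope, qualifying value reused.** The times 0, 1, 3, 6 have mean 2.5 and sum of squares 6.25 + 2.25 + 0.25 + 12.25 = 21. The weight on month 0 is -2.5/21 per month, or -30/21 = -1.43 per year. Spurious slowing = (2 + 1.43)σ²λ/V, which is 1.71 times the fresh figure.

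**Worked example (μ = -2, σ = 3).** V = √27 = 5.196, c = 0.192, λ = 0.924. True slope = -2 - 9 × 0.924/5.196 = -3.6. Prior-slope bias = -18 × 0.924/5.196 = -3.2, so the prior slope is -6.8. On-study slope is -3.6 if month 0 is fresh, and -3.6 + 1.43 × 1.60 = -1.3 if reused.

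**Expected spurious slowing (mL/min/1.73m² per year), fresh / reused:**

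| σ | μ = -2 | μ = -3 | μ = -5 |
|---|---|---|---|
| 1 | 0.6 / 1.0 | 0.5 / 0.8 | 0.3 / 0.5 |
| 2 | 1.9 / 3.2 | 1.5 / 2.7 | 1.0 / 1.7 |
| 3 | 3.2 / 5.5 | 2.8 / 4.7 | 2.0 / 3.4 |
| 4 | 4.5 / 7.7 | 4.0 / 6.8 | 3.1 / 5.2 |

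With σ = 0 the artefact is zero. A simulation that also imposed the eGFR entry range of 20 to below 60 agreed within about 0.3 throughout.

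**How often it would mislead.** In simulated null trials with 44 per arm, slope SD 3, σ = 2 to 4 and a fresh month 0, a single arm showed significant slowing (paired t-test) in 14 to 48% of trials, against a nominal 2.5% in that direction. Both arms did so in 2 to 23%. At σ = 1 the single-arm figure was 7 to 17%. If the qualifying value was reused for everyone, it was 26 to 82% for σ = 2 to 4. The between-arm slope test rejected in about 4 to 6% of trials in every setting, against a target of 5%.

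**The case against.** **The analysis is exploratory and sits beside an unbiased one.** This stands. Both places that plan it call it exploration, and both name the between-group slope comparison first. A reader might infer that the trial would confirm slower progression even if Avmacol did nothing. The documents do not support that: they describe a randomised, placebo-controlled test and nowhere say that the within-group result alone supports efficacy. The placebo arm would show the same artefact.

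**The bias is an expectation, not a certain result.** This also stands. It would be too strong to say that both arms will show slowing. With a fresh month 0 and slope SD 3, both arms moved in the favourable direction in 66 to 95% of simulated trials at σ = 2 to 4, but in only 48 to 71% at σ = 1.

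**The size depends on assumptions.** True. The two-point rule is one of them, and Aim 1's wording may suggest more values. Selecting on a five-value slope (every 3 months) changes the spurious slowing to 1.6σ²λ/V with V = √(9 + 1.6σ²). At μ = -3, σ = 3 this gives 2.4 instead of 2.8, so the bias shrinks but remains. The documents also do not say which values form the previous 6 months. If a fresh month-0 value were averaged with the qualifying value at the same time point, the fresh figures would halve.

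**Reuse of the qualifying value is not planned.** Correct. Baseline blood is scheduled, so the fresh figures are the main ones. Reuse is possible for some patients: the notes in Section 8 let routine results come from the medical record and limit the extra sample to biomarkers when routine labs were done elsewhere, and the baseline row of the Schedule of Assessments only asks that eGFR be noted.

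**Biomarkers.** A reader might extend the argument to within-group biomarker change from baseline. Eligibility does not select on any biomarker, so this mechanism does not carry over.

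**Conclusion.** The point holds for one stated exploratory analysis. As planned, the comparison of on-study eGFR slope with the previous 6 months within each group is biased by regression to the mean toward apparent slowing in both arms, and nothing in the documents corrects for it.

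Under the stated assumptions the expected artefact is about 0.3 to 4.5 mL/min/1.73m² per year with a fresh month-0 value (1.0 to 4.5 for σ = 2 to 4). For patients whose qualifying eGFR is reused it is about 0.5 to 7.7. At the upper end this exceeds the entry threshold of 3 per year. The direction follows from the design whenever eGFR varies between visits and the qualifying value enters the prior slope; the size cannot be fixed from the documents. The primary outcome and the randomised between-group slope comparison are not affected.

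**What to change.** In Section 4 (Aim 2) and Section 18 (Statistical Analysis):

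- Base any statement about an Avmacol effect on eGFR progression only on the between-arm difference in on-study slope.
- Drop the within-group comparison with the previous 6 months as an efficacy analysis. Alternatively, keep it as descriptive only, shown for both arms, with a note that regression to the mean is expected.
- State that month 0 in the slope model is the eGFR from the baseline-visit sample, not the qualifying value.

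The cost is mostly wording. One exploratory within-arm inference is lost, and an occasional study-paid baseline metabolic panel may be needed where routine labs were done before the visit. Enrolment, sample size and treatment do not change.
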